## **Physical Description of Study Interventions**

The JNJ-3989 supplied for this study will be provided as an aqueous clear, colorless to light yellow solution with 200 mg/mL of JNJ-3989 for subcutaneous injection, CCI

JNJ-3989 will be manufactured and provided under the responsibility of the sponsor. Refer to the IB for a list of excipients. 

NA (tenofovir disoproxil) and PegIFN- $\alpha$ 2a treatment will be provided by the sponsor. Refer to the prescribing information for a list of excipients.

Tenofovir disoproxil is formulated as oral film-coated tablet of 245 mg strength.

PegIFN- $\alpha$ 2a formulated as solution for subcutaneous injection in a prefilled syringe with 180  $\mu$ g/0.5 mL of PegIFN- $\alpha$ 2a, will be provided by the sponsor. Refer to the prescribing information for a list of excipients.

# **Packaging and Labeling**

All study interventions will be packaged with each unit labeled with a unique medication ID number. Commercial supplies of tenofovir disoproxil and PegIFN- $\alpha$ 2a will be sourced and a clinical study label will be applied. Study intervention labels will contain information to meet the applicable regulatory requirements.

NA (tenofovir disoproxil) and PegIFN- $\alpha$ 2a treatment may also be repackaged into child-resistant packaging if this is not already the case.

No study interventions can be repacked or relabeled without prior approval from the sponsor.

#### **Study Intervention Administration**

Study intervention administration must be captured in the source documents and the CRF.

JNJ-3989 injections will be administered subcutaneously (preferably in the abdomen) at the study site.

NA and PegIFN- $\alpha$ 2a treatment will be provided by the sponsor. Investigators should follow guidance detailed in the respective prescribing information, including special warnings and precaution for use.

In between study visits, participants will take their NA orally at home and they will bring their NA with them to each study visit. Study-site personnel will instruct participants on how to take their NA orally at home. At study visits, NA should be taken on site to allow biochemistry and renal biomarker samples to be taken in fasted conditions.

For PegIFN- $\alpha$ 2a, administration should be done SC in the thigh or abdomen, preferably in the evening by self-injection. Used PegIFN- $\alpha$ 2a syringes should be separated from the needle via the sharps container and then placed into their original box and returned to the site, if allowed per local guidelines and regulations. The used needles in the sharps container will be returned to the study site after completion of the consolidation phase or disposed of following local standard procedures. If desired, participants can also choose to have the weekly administration of PegIFN- $\alpha$ 2a performed at the study site irrespective of the time of day.

JNJ-3989 and PegIFN- $\alpha$ 2a should be injected subcutaneously into different areas of the abdomen and approximate location should be recorded.

For a definition of study intervention overdose, refer to Section 8.4, Treatment of Overdose.

## 6.2. Preparation/Handling/Storage/Accountability

#### Preparation/Handling/Storage

All study interventions must be stored as specified on the product specific labeling.

Study-site personnel will instruct participants on how to store study intervention for at home use as indicated for this protocol.

Refer to the pharmacy manual/study site investigational product and procedures manual for additional guidance on study intervention preparation, handling, and storage.

## **Accountability**

The investigator is responsible for ensuring that all study intervention received at the site is inventoried and accounted for throughout the study. The dispensing of NA (tenofovir disoproxil) and PegIFN- $\alpha$ 2a (if applicable) to the participant, and the return of JNJ-6379, NA (tenofovir disoproxil), and PegIFN- $\alpha$ 2a from the participant (if applicable), must be documented on the intervention accountability form. Participants must be instructed to return all original containers, whether empty or containing study intervention. The JNJ-3989 and PegIFN- $\alpha$ 2a injections administered to the participant must be documented on the intervention accountability form. All study intervention will be stored and disposed of according to the sponsor's instructions. Study-site personnel must not combine contents of the study intervention containers.

Participants who stopped JNJ-6379 per Protocol Amendment 6, must return their JNJ-6379 supply at the next scheduled visit. The return of JNJ-6379 from the participant must be documented on the intervention accountability form.

Study intervention must be handled in strict accordance with the protocol and the container label, and must be stored at the study site in a limited-access area or in a locked cabinet under appropriate environmental conditions. Unused study intervention, and study intervention returned by the participant, must be available for verification by the sponsor's study site monitor during on-site monitoring visits. The return to the sponsor of unused study intervention, or used returned study intervention for destruction, will be documented on the intervention return form. When the study

site is an authorized destruction unit and study intervention supplies are destroyed on-site, this must also be documented on the intervention return form.

Potentially hazardous materials containing hazardous liquids, such as used ampules, needles, and vials, should be disposed of immediately in a safe manner and therefore will not be retained for intervention accountability purposes. Details on handling of used PegIFN- $\alpha$ 2a syringes are described in Section 6.1, Study Intervention(s) Administered.

Study intervention should be dispensed under the supervision of the investigator or a qualified member of the study-site personnel, or by a hospital/clinic pharmacist. Study intervention will be supplied only to participants participating in the study. Returned study intervention must not be dispensed again, even to the same participant. Whenever a participant brings his or her oral study intervention to the study site for pill count, this is not seen as a return of supplies. Study intervention may not be relabeled or reassigned for use by other participants. The investigator agrees neither to dispense the study intervention from, nor store it at, any site other than the study sites agreed upon with the sponsor. Further guidance and information for the final disposition of unused study interventions are provided in the Study Reference Manual.

## 6.3. Measures to Minimize Bias: Randomization and Blinding

#### **Intervention Allocation**

### Procedures for Randomization and Stratification

As of Protocol Amendment 6, randomization will not be used in this study. All participants will be assigned to receive JNJ-3989 + NA + PegIFN- $\alpha$ 2a by the interactive web response system (IWRS).

Prior to Protocol Amendment 6, randomization and stratification were performed as described below.

Central randomization was implemented in this study. Participants were randomly assigned in a 1:1 ratio to 1 of 2 intervention arms based on a computer-generated randomization schedule prepared before the study by or under the supervision of the sponsor. The randomization was balanced by using randomly permuted blocks and was stratified by screening HBV DNA level ( $\geq 10^7 \text{ IU/mL OR} < 10^7 \text{ IU/mL}$ ) and race (Asian versus non-Asian; for participants in Cohort 2).

For more information on the interactive web response system (IWRS), refer to Section 6.3 of the Master Protocol PLATFORMPAHPB2001.

#### **Blinding**

As this is an open-label study, blinding procedures are not applicable.

## 6.4. Study Intervention Compliance

JNJ-3989 will be administered at the study site as a subcutaneous injection by qualified study-site personnel to assure compliance with study requirements.

The participants will be requested to bring unused study interventions and empty packaging to the study site at each visit.

Every effort should be made to have the participant take the study interventions as indicated in the Schedule of Activities.

- If an injection of JNJ-3989 was missed, the injection should be given as soon as possible but within 3 weeks after the scheduled time. Otherwise, the injection should be skipped and the next injection should be given at the next scheduled time point per the initial injection schedule.
- If a dose of NA is missed, the participant should follow the guidelines in the prescribing information.
- If an injection of PegIFN- $\alpha$ 2a is missed, the participant should follow the guidelines in the prescribing information.

If a participant's study intervention intake is not according to the protocol, the investigator will take the necessary measures to ensure future adherence to the protocol.

An optional medication diary to document study intervention intake can be made available for participants with an observed or known risk for study intervention non-compliance. The completed diaries are reviewed by the site staff and discussed with the participants for compliance monitoring and counseling. Completed diaries will be returned to the site staff to add to the source documents.

## 6.5. Concomitant Therapy

*Note:* With the removal of JNJ-6379 as study intervention in Protocol Amendment 6, JNJ-6379-specific disallowed medications and concomitant medications to be used with caution are no longer applicable and have been removed.

An overview of ISA-specific disallowed medication is provided in Table 3.

Local guidelines on the use of live vaccines in participants receiving PegIFN- $\alpha$ 2a should be followed, including for the second dose of Sputnik V (which contains rAd5, with a theoretical risk of replication competence). Sputnik Light, which is the first dose of Sputnik V (with rAd26) is not considered a live vaccine. See below for further guidance on the use of COVID-19 vaccines.

Note that locally approved COVID-19 vaccines (including those that received emergency use authorization or conditional marketing authorization) are allowed throughout the study. The following recommendations should be applied to accommodate COVID-19 vaccination during the consolidation phase:

- COVID-19 vaccine and PegIFN- $\alpha$ 2a should not be administered on the same day.
- If required, PegIFN- $\alpha$ 2a injection can be delayed with 2 days. The next PegIFN- $\alpha$ 2a injection should be performed at the scheduled time.

- If required, skipping a PegIFN- $\alpha$ 2a injection may be considered after consultation with the Sponsor.
- Vaccination with Sputnik V should take above-mentioned consideration about live vaccines into account.

All COVID-19 vaccination-related data (eg, COVID-19 vaccination, AEs, AE management) should be appropriately captured in the CRF and source documents. Refer to the COVID-19 vaccine and/or PegIFN-α2a prescribing information for more details.

For general concomitant therapy considerations, refer to Section 6.5 of the Master Protocol PLATFORMPAHPB2001.

#### **Table 3: Disallowed Medication**

#### Disallowed at any time prior to screening until end of follow-up:

• Any HBV antiviral medicines (including vaccines, NAs, and IFN products) other than the study intervention taken in the context of this study.

*Note*: Prior hepatic treatment with herbal or nutritional products is allowed but should be stopped at screening.

**Note**: <9 months of prior NA treatment is allowed but should have ended at least 12 months before screening.

#### Disallowed from 6 months prior to screening until end of follow-up:

Any investigational agent, investigational vaccine, invasive investigational medical device, or
investigational biological product (other than the study intervention taken in the context of this study).
 Note: For investigational COVID-19 vaccines administered within 6 months prior to screening, an
exception will be made as long as the vaccine has been approved (or received emergency use authorization
or conditional marketing authorization) at the time of screening.

#### Disallowed from 6 months prior to baseline until end of follow-up:

• Any systemically (eg, intravenously, intramuscularly, orally, subcutaneously) administered medication that directly or indirectly interferes with immune responses (eg, cyclosporine, interleukins, programmed death-[ligand] 1 inhibitors, systemic corticosteroids exceeding 5 mg of prednisolone equivalent/day).

#### Disallowed from screening until end of follow-up:

- Biotin (>1 mg daily dose), either taken alone or as part of a multivitamin formulation. *Note:* The use of other vitamins is allowed.
- Topical steroids (>7 days) under occlusive dressing.

**Note:** The list of disallowed concomitant medication is not exhaustive; for products falling in one of the categories and not mentioned by name, the sponsor should be contacted to determine whether the product can be allowed.

The prescribing information for tenofovir disoproxil and PegIFN- $\alpha$ 2a should be consulted for any additional prohibited medication. In case of flu-like symptoms after administration of PegIFN- $\alpha$ 2a, paracetamol up to a maximum of 2 g per 24 hours and a maximum of 6 g per week is allowed.

Medications requiring subcutaneous injection (other than JNJ-3989 and PegIFN- $\alpha$ 2a; eg, insulin) should be administered away from the JNJ-3989 and PegIFN- $\alpha$ 2a injection sites.

#### 6.6. Dose Modification

Dose modifications of JNJ-3989 and NA (increase or decrease of dose level) are not permitted during the study.

For PegIFN- $\alpha$ 2a, dose adjustment guidelines are applicable for participants who develop laboratory abnormalities during PegIFN- $\alpha$ 2a treatment, as recommended in the locally approved prescribing information for PegIFN- $\alpha$ 2a and upon investigator's assessment. The guidance from the Pegasys USPI has been provided as an example (see Table 4).

Table 4: PegIFN-α2a Hematological Dose Modification Guidelines

Laboratory Values	Recommended Dose
ANC <750 cells/mm 	Reduce to 135µg
ANC <500 cells/mm 	Discontinue treatment until ANC values return to more than 1,000 cells/mm  .
	Reinstitute at 90µg and monitor ANC.
Platelet <50,000 cells/mm 	Reduce to 90µg
Platelet <25,000 cells/mm 	Discontinue treatment

ANC: absolute neutrophil count

Source: Pegasys USPI

For participants who prematurely discontinue PegIFN- $\alpha$ 2a, treatment with PegIFN- $\alpha$ 2a may be restarted according to the recommendations from the locally approved prescribing information for PegIFN- $\alpha$ 2a.

## 6.6.1. Study Intervention Completion at Consolidation Week 12

With the implementation of Protocol Amendment 6, all participants had to stop JNJ-6379 treatment immediately.

Participants will complete treatment with JNJ-3989 and PegIFN-α2a at the end of the consolidation phase (Consolidation Week 12). If all of the following NA treatment completion criteria are met at consolidation Week 12, NA will also be stopped at the next scheduled visit (ie, at FU Week 2):

- The participant has ALT <3x ULN, AND
- The participant has HBV DNA <LLOQ, AND
- The participant is HBeAg-negative, AND
- The participant has HBsAg <10 IU/mL.

**Note:** In case of ALT elevation ≥3x ULN at consolidation Week 12, the investigator must consider different potential causes of increased ALT to ensure appropriate work up and management as needed. If the ALT elevation is unrelated to HBV activity and/or <3x ULN by FU Week 2, NA completion may be considered at the discretion of the investigator and in consultation with the sponsor.

Participants who do not meet the above criteria at consolidation Week 12 should continue NA treatment during the 48-week follow-up.

The investigator should consider to re-start NA treatment per local standard of care at the EOS visit (Follow-up Week 48) for participants who met the NA treatment completion criteria at Consolidation Week 12, who did not re-start NA treatment during the follow-up phase, and who did not achieve and maintain HBsAg seroclearance. NA will not be provided by the sponsor after the final study visit.

If a participant prematurely (before the end of the consolidation phase) discontinues JNJ-3989, follow-up assessments should be obtained as per the Schedule of Activities until 48 weeks after the end of investigational intervention unless the participant withdraws consent. If a participant prematurely discontinues PegIFN-α2a (before the end of the consolidation phase), treatment with JNJ-3989 and NA should be continued as planned. In case the participant withdraws consent, NA treatment may be continued or, in consultation with the sponsor, discontinued, based on the above mentioned NA treatment completion criteria.

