- The participant has confirmed ≥Grade 3 hematologic abnormalities as described in Section 8.3.6.4, Hematologic abnormalities.

*Note:* The grades are based on the DAIDS Toxicity Grading Scale (see Section 10.9, Appendix 9, DAIDS Table).

In addition, PegIFN- $\alpha$ 2a during consolidation phase must immediately be discontinued for any of the following reasons:

- Participant has platelet count <25,000 cells/mm^3
- Participant has ANC <500 cells/mm^3 Note: PegIFN-α2a treatment can be restarted when ANC values return to more than 1,000 cells/mm^3 (see details in Section 6.6, Dose Modification)
- Participant develops evidence of hepatic decompensation during treatment, or ALT increase clinically significant or accompanied by direct bilirubin increase
- Participant develops thyroid disorders or diabetes during treatment and cannot be controlled with medication
- Participant develops new or worsening ophthalmologic disorders
- Participant develops any deterioration of cardiovascular status
- Participant develops serious, acute hypersensitivity reaction (e.g., urticaria, angioedema, bronchoconstriction, anaphylaxis)
- Participant develops serious infection (bacterial, viral, fungal) and sepsis
- Participant develops persistent or unexplained pulmonary infiltrates or pulmonary function impairment
- Participant with onset or worsening of psoriatic lesion
- Participant develops moderate or severe depression, or other psychiatric symptoms (for mild depression, treatment discontinuation may be considered)

*Note:* Participants who develop a neuropsychiatric AE during PegIFN- $\alpha$ 2a treatment, will be monitored closely until the neuropsychiatric AE resolves, with frequent (at least weekly) follow-up phone calls.

- Participant develops colitis symptoms (such as but not limited to abdominal pain, bloody diarrhea, and fever)
- Participant develops symptoms or signs suggestive of pancreatitis

For participants who prematurely discontinue PegIFN- $\alpha$ 2a, treatment with PegIFN- $\alpha$ 2a may be restarted according to the recommendations from the locally approved prescribing information for PegIFN- $\alpha$ 2a.

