Hemoglobin t , Low (g/dL; mmol/L) u aged ≥13 years (male only)	10.0 to 10.9 6.19 to 6.76	9.0 to <10.0 5.57 to <6.19	7.0 to <9.0 4.34 to <5.57	<7.0 <4.34
aged ≥13 years (female only)	9.5 to 10.4 5.88 to 6.48	8.5 to <9.5 5.25 to <5.88	6.5 to <8.5 4.03 to <5.25	<6.5 <4.03
aged 57 days to <13 years (male and female)	9.5 to 10.4 5.88 to 6.48	8.5 to <9.5 5.25 to <5.88	6.5 to <8.5 4.03 to <5.25	<6.5 <4.03
aged 36 to 56 days (male and female)	8.5 to 9.6 5.26 to 5.99	7.0 to <8.5 4.32 to <5.26	6.0 to <7.0 3.72 to <4.32	<6.0 <3.72
aged 22 to 35 days (male and female)	9.5 to 11.0 5.88 to 6.86	8.0 to <9.5 4.94 to <5.88	6.7 to <8.0 4.15 to <4.94	<6.7 <4.15
aged 8 to ≤21 days (male and female)	11.0 to 13.0 6.81 to 8.10	9.0 to <11.0 5.57 to <6.81	8.0 to <9.0 4.96 to <5.57	<8.0 <4.96
aged ≤7 days (male and female)	13.0 to 14.0 8.05 to 8.72	10.0 to <13.0 6.19 to <8.05	9.0 to <10.0 5.59 to <6.19	<9.0 <5.59

HIV: human immunodeficiency virus; LLN: lower limit of normal

s Revised by the sponsor.

Male and female sex are defined as sex at birth. For transgender participants aged ≥13 years who have been on hormone therapy for more than 6 consecutive months, grade hemoglobin based on the gender with which they identify (ie, a transgender female should be graded using the female sex at birth hemoglobin laboratory values).

The most commonly used conversion factor to convert g/dL to mmol/L is 0.6206. For grading hemoglobin results obtained by an analytic method with a conversion factor other than 0.6206, the result must be converted to g/dL using the appropriate conversion factor for the particular laboratory.

	LABORATORY VALUES			
		HEMATOLOGY		
PARAMETER	GRADE 1 MILD	GRADE 2 MODERATE	GRADE 3 SEVERE	GRADE 4 POTENTIALLY LIFE- THREATENING
INR, High (not on anticoagulation therapy)	1.1 to <1.5×ULN	1.5 to <2.0×ULN	2.0 to <3.0×ULN	≥3.0×ULN
Methemoglobin (% hemoglobin)	5.0% to <10.0%	10.0% to <15.0%	15.0% to <20.0%	≥20.0%
PTT, High (not on anticoagulation therapy)	1.1 to <1.66×ULN	1.66 to <2.33×ULN	2.33 to <3.00×ULN	≥3.00×ULN
Platelets, Decreased (cells/mm³; cells/L)	100,000 to <125,000 100.000×10  to <125.000×10 	50,000 to <100,000 50.000×10  to <100.000×10 	25,000 to <50,000 25.000×10  to <50.000×10 	<25,000 <25.000×10 
PT, High (not on anticoagulation therapy)	1.1 to <1.25×ULN	1.25 to <1.50×ULN	1.50 to <3.00×ULN	≥3.00×ULN

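### A confirmed Grade 3 or higher platelet or neutrophil count meets three unaligned instructions in the protocol, and Section 7.1 conflicts with itself over whether JNJ-3989 continues

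*Protocol*

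**What the plan says.** **Section 6.6, Table 4.** PegIFN adjustment follows the locally approved prescribing information and the investigator's assessment. The table's status is stated: "The guidance from the Pegasys USPI has been provided as an example (see Table 4". For platelets, PegIFN is reduced to 90 µg in the row "Platelet <50,000 cells/mm" and stopped in the row "Platelet <25,000 cells/mm". For neutrophils, it is reduced to 135 µg in the row "ANC <750 cells/mm". Below 500 the entry is "Discontinue treatment until ANC values return to more than 1,000 cells/mm", followed by a restart at 90 µg.

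**Section 7.1, general list.** The lead-in makes discontinuation of JNJ-3989 and PegIFN mandatory for the reasons listed. One of them is: "The participant has confirmed ≥Grade 3 hematologic abnormalities as described in Section 8.3.6.4". A note under the list says that grades are on the DAIDS scale.

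**Section 7.1, PegIFN-only list.** PegIFN must be stopped immediately when "Participant has platelet count <25,000 cells/mm" applies, or when neutrophils fall below 500. The neutrophil entry allows a restart above 1,000 and refers back to Section 6.6. The opening of Section 7.1 says that if PegIFN alone is stopped, JNJ-3989 goes on; Sections 4.1 and 6.6.1 repeat this.

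**Section 8.3.6.4.** For confirmed Grade 3 or 4 hematologic abnormalities, stopping JNJ-3989 and PegIFN is to be considered. A confirmatory visit is wanted preferably within 7 days of receiving the first result.

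**Appendix 9 (DAIDS).** Grade 3 platelets are "25,000 to <50,000", and lower counts are Grade 4. Grade 3 neutrophils are 400 to 599, and lower counts are Grade 4.

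**The concern.** These passages address the same blood counts with instructions of different force and scope. Platelet reduction is described as a common reaction to PegIFN (Section 2.2.2.3), and hematologic abnormalities are an event of special interest (Section 8.3.6), so the situation is foreseeable.

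Two sites reading different passages could treat the same confirmed count differently. One would continue the regimen, with adjusted or interrupted PegIFN, to consolidation Week 12. The other would stop both drugs and move the participant into the 48-week follow-up. That affects exposure to a drug with known marrow effects. It also moves the date from which follow-up visits are counted, and it can decide whether the participant stays in the per-protocol set.

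**Working it through.** There is no sample size or power figure to reproduce. The check lays the Table 4 limits over the DAIDS grades and reads off the Section 7.1 consequence. Inputs are Section 6.6 Table 4, Section 7.1 (both lists and the lead-in), Section 8.3.6.4 and Appendix 9. Counts are per mm³.

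| Count | DAIDS grade | Table 4 for PegIFN | Section 7.1 PegIFN-only list | Section 7.1 general list, once confirmed |
|---|---|---|---|---|
| Platelets 50,000 to <100,000 | 2 | no change | not triggered | not triggered |
| Platelets 25,000 to <50,000 | 3 | reduce | not triggered | stop both |
| Platelets <25,000 | 4 | stop | stop PegIFN; JNJ-3989 continues | stop both |
| Neutrophils 600–749 | 2 | reduce | not triggered | not triggered |
| Neutrophils 500–599 | 3 | reduce | not triggered | stop both |
| Neutrophils 400–499 | 3 | interrupt, restart | stop PegIFN, restart allowed; JNJ-3989 continues | stop both |
| Neutrophils <400 | 4 | interrupt, restart | stop PegIFN, restart allowed; JNJ-3989 continues | stop both |

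In every Grade 3 or 4 row, Section 8.3.6.4 adds that stopping both is to be considered.

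**Reduced-dose conflict.** The whole platelet reduction range lies in Grade 3. For neutrophils only 500–599 of the 500–749 range does; 600–749 is Grade 2 and does not conflict.

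**Conflict inside Section 7.1.** Platelets below 25,000 and neutrophils below 500 are all Grade 3 or 4. The PegIFN-only list, read with the section's opening, leaves JNJ-3989 running there, and for neutrophils allows PegIFN to resume. The general criterion stops both. This does not depend on Table 4.

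**Effect on time points.**
- The follow-up schedule counts visits from the last JNJ-3989/PegIFN dose (Section 1.3.2, footnote a).
- SAP Table 1 ends consolidation at JNJ-3989 discontinuation if that comes first, with a 5-day addition where its footnote applies, and starts follow-up the next day.
- Consolidation lasts 12 weeks, and the first scheduled hematology after PegIFN starts is consolidation Week 2. The largest shift on scheduled visits is therefore 12 − 2 = 10 weeks. A confirmatory visit about a week later makes it 12 − 2 − 1 = 9 weeks.

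**Effect on analysis sets.** SAP Attachment 1 row 58 excludes from the per-protocol set, without condition, anyone who met a discontinuation criterion and did not stop. A site that follows Table 4 after a confirmed Grade 3 platelet count would create such an exclusion if the mandatory wording governs, and would not if the Section 8.3.6.4 wording governs. The ITT set requires only one consolidation-phase dose, so it is unaffected.

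**The case against.** The strongest reply is that the Section 7.1 criterion is not free-standing. It cites Section 8.3.6.4, where stopping is only to be considered, and considering a stop is compatible with reducing PegIFN meanwhile. Other entries in the same list are softened despite the mandatory lead-in: virologic breakthrough does not stop treatment automatically, and treatment can continue after some Grade 3 eGFR findings. Table 4 is an example subordinate to local labels and clinical judgement. The triggers also differ, since Table 4 states no confirmation requirement. A site could adjust on the first value, stop PegIFN at once below the lower limits, and decide on both drugs after confirmation.

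Much of this stands. A reader might infer that one blood count always produces opposite orders, to reduce or to stop. The documents do not support that, because Section 8.3.6.4 sits between the two, Table 4 is not a fixed instruction, and the general criterion needs confirmation.

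What does not stand is the conclusion that nothing is left to fix. The softening for breakthrough and eGFR is written into those entries; the hematologic entry carries only a cross-reference, under a lead-in of different force. The layered sequence is stated nowhere. Nor does it explain how JNJ-3989 can continue and PegIFN resume after a confirmed neutrophil count below 500 when the general criterion stops both.

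**Conclusion.** The point holds as a misalignment of three instructions (stop both, consider stopping both, continue PegIFN reduced) for confirmed platelets of 25,000 to <50,000 and neutrophils of 500–599. It also holds as a contradiction within Section 7.1 over JNJ-3989, and over the neutrophil restart, at platelets <25,000 and neutrophils <500.

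The size is modest. The conflict begins only at confirmation, and the documents do not say how often it will arise; the widths of the count ranges say nothing about numbers of participants. A shift of the full 12 weeks might be inferred from the length of consolidation, but the visit schedule supports at most about 10, assuming the count is first seen at consolidation Week 2 with no earlier unscheduled test.

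The primary ITT set does not change. The calendar timing of FU Week 24 for affected participants, and membership of the per-protocol set, do depend on which passage the site followed. The per-protocol analysis of the primary endpoint is descriptive and uses observed cases (SAP Section 5.2.4), so the effect there is secondary. The safety aspect is the better reason to correct the text.

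**What to change.** Reconcile Section 6.6 with Table 4, both lists in Section 7.1, Section 8.3.6.4 and the DAIDS grades. Each platelet and neutrophil range, with its confirmed or unconfirmed status, should lead to one consistent instruction for PegIFN and one for JNJ-3989. State how local prescribing information ranks against Section 7.1, and whether discontinuation at confirmed Grade 3 or higher is mandatory or to be considered. Section 8.3.6.4 must be part of the change; otherwise its wording would still differ from whatever rule is adopted. Then align SAP Attachment 1 row 58 with that rule, so that a site following the protocol is not recorded as having failed to stop treatment. Which rule is clinically right is for the sponsor to decide.

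The cost is a text clarification in the protocol and the SAP, with no new procedures or visits.
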